5 STUDY DESIGN

5.1 Study description

AS0009 is a multicenter OLE study to assess the long-term safety, tolerability, and efficacy of bimekizumab in eligible adult subjects with AS who completed the Phase 2b study AS0008. At Week 48 of AS0008, all subjects continuing into AS0009 will undergo the final AS0008 study assessments and any nonoverlapping AS0009 entry assessments, and will then receive their first open-label dose of bimekizumab.

The OLE study will assess the safety, tolerability, and efficacy of bimekizumab for a period of up to 204 weeks (~4 years). Bimekizumab will be administered at a dose of 160mg Q4W upon entry into AS0009, regardless of the dose received in AS0008.

Additionally, as described in ([Section 5.1.1](#)), other treatments may be used in addition to bimekizumab per Investigator discretion. Subjects not responding to treatment may be withdrawn from the treatment and study at the discretion of the Investigator.

Following study completion or early termination, subjects will return for a SFU Visit 20 weeks after their last dose of bimekizumab.

Schedules of study assessments are presented in [Table 5–1](#) and [Table 5–2](#).

A study schematic diagram of AS0009 is presented in [Figure 5–1](#).

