3.5 Mapping of assessments

Study assessments at an Early Termination (ET) visit where the visit date is within the protocol-defined visit window of a scheduled site visit will be mapped to that scheduled site visit (this does not include home visits). Visit windows will be calculated relative to the date of first dose in AS0009 (planned at the AS0009 EV), but if the dose was missed at that visit, the date of the AS0009 EV will be used instead. The following rules will also be applied:

- If there is an existing scheduled site visit in the window, and the specific assessment was performed at that scheduled site visit, then the relevant assessments at the ET visit will be mapped to the next scheduled site visit (regardless of whether this is within the protocol-defined visit window for that site visit).
- Study assessments at an ET visit that does not fall into the protocol-defined visit window of a scheduled site visit will be assigned to the next scheduled site visit after the date of the ET visit (regardless of whether this is within the protocol-defined visit window for that site visit).
- Mapping of an assessment to a scheduled visit will occur regardless of whether the assessment was planned to be conducted at that visit (with the exception of ADAb). For ADAb however, data will only be mapped to scheduled site visits where ADAb levels are planned to be measured. Any PK samples taken at the same ET visit will be mapped to the same scheduled visit as the ADAb.

- Additional rules regarding visit mapping are provided in [Section 8.1.5](#) for BASMI and [Section 9.1](#) and [Section 9.2](#) for PK and ADA_b summaries respectively.

Unscheduled assessments where the visit date is within the protocol-defined visit window of a scheduled site visit will be mapped to that scheduled site visit (this does not include home visits). Visit windows will be calculated relative to the date of first dose in AS0009. But if the dose was missed at that visit, the date of the AS0009 EV will be used instead. The following rules will also be applied:

- If there is an existing assessment with a non-missing response (from a scheduled site visit or ET visit) in the window, the assessment will be left as unscheduled.
- Unscheduled assessments which do not fall within a protocol-defined visit window based on time since first dose (or date of AS0009 EV if the first dose was missed) will be left as unscheduled.

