4.2 Handling of dropouts or missing data

4.2.1 Handling of missing data for efficacy analysis

Calculation of derived efficacy variables in the presence of missing data is described in individual sub-sections of [Section 8.1](#). All derived efficacy variables will be calculated using observed data, and any resulting missing data will be handled as described in this section. All non-responder imputation (NRI) and multiple imputation (MI) as described below will be performed only for subjects in the FAS for AS0009.

For assessments missing during AS0008 which are used in AS0009 for reporting maintenance of response, the imputed value (based on NRI) from the AS0008 database will be used.

For all visits in AS0009 (including AS0009 EV), missing values or values which cannot be constructed due to missing components for binary secondary/other efficacy variables (ASAS40, ASAS20, ASAS5/6) will be imputed using NRI. For each visit, subjects with missing data or who have dropped out of the study will be counted as non-responders. This includes any subjects with missing baseline values.

For missing continuous secondary/other efficacy variables an MI approach will be used. This will be performed for the following variables/endpoints:

- ASAS components:
 - Total Spinal Pain, Question 1 from TNSP
 - Inflammation, derived as the mean of Question 5 and 6 from the BASDAI
- ASDAS-CRP components:

- Total Back Pain, Question 2 from the BASDAI
- Duration of Morning Stiffness, Question 6 from the BASDAI
- PGADA (this is already included below as this is required as a standalone endpoint)
- Peripheral Pain/Swelling, Question 3 from the BASDAI
- CRP

ASDAS-CRP and ASDAS-ID will be determined after MI of the individual components of the ASDAS-CRP (ie, MI will not be applied to the overall ASDAS-CRP score). Note that for CRP the rules for handling measurements that are below the limit of quantification (BLQ) should be followed as per [Section 8.1.2](#). Thus, if any imputed values are <2mg/L these will be replaced with a constant value of 2mg/L for subsequent derivation of ASDAS-CRP. For the ASDAS-ID, the number of subjects within each disease activity category will be derived for each imputation and the mean number of subjects within each category across imputations will be presented.

- BASDAI
- BASFI
- BASMI
- MASES

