In the event that $\geq 10\%$ of subjects in either treatment group are classified as Category 5 the figure will be repeated by treatment at completion of AS0008 and overall and by ADAb status (6 lines per plot). This will be implemented for both plots (considering only AS0009 and considering data from both AS0008 and AS0009).

An additional figure will be presented considering data from both AS0008 and AS0009, and will be presented by actual treatment at randomization in AS0008 only. This figure will be presented as follows:

- If $<10\%$ of subjects in each treatment group (based on treatment at randomization) are classified as Category 5, the figure will be presented with 5 lines on 1 plot (1 for each treatment) and both categories combined
- If $\geq 10\%$ of subjects in any treatment group (based on treatment at randomization) are classified as Category 5, the figure will be presented by category and treatment at randomization with separate plots (each with 5 lines) for each category
- A summary of efficacy response (ASAS40 responders [based on NRI]) as a function of ADAb titer will be presented graphically. The x-axis will display the ADAb titer at the AS0009 Week 48 time point (categorized as negative, Q1, Q2, Q3 and Q4 where the latter represents the quartiles for the ADAb titers at Week 48) and the y-axis will display percentage of ASAS40 responders at the Week 48 time point within each titer category.

Subjects with negative ADAb results at the Week 48 time point will be included in the ‘negative’ category on the x-axis; subjects with missing ADAb data at the Week 48 time point will be excluded from the plot. The figure will be based on the FAS.

- A summary of efficacy response (ASAS40 responders) versus time will be presented graphically including the following ADAb groups (3 lines per plot):
 - ADAb positive
 - Defined as subjects having at least 2 ADAb positive samples during AS0009 (including AS0009 EV and excluding SFU) regardless of other ADAb negative samples and/or missing or inconclusive samples
 - ADAb negative

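### The Week 48 ASAS40-by-ADAb-titer figure leaves most subjects who withdraw before about Week 36 out of its NRI denominator, so response is shown too high and a titer-related loss of response can be misstated

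*SAP*

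**What the plan says.** SAP 9.2 plans this figure: "A summary of efficacy response (ASAS40 responders [based on NRI]) as a function of ADAb titer will be presented graphically". The horizontal axis is the ADAb category at AS0009 Week 48 (negative, then four quartile groups of titer). The vertical axis is the percentage of ASAS40 responders at the same visit. On the analysis set it says "The figure will be based on the FAS", and on missing samples "subjects with missing ADAb data at the Week 48 time point will be excluded from the plot".

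The NRI rule in SAP 4.2.1 reads "For each visit, subjects with missing data or who have dropped out of the study will be counted as non-responders".

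Under SAP 3.5, assessments from an early termination (ET) visit outside any visit window "will be assigned to the next scheduled site visit after the date of the ET visit". There is a restriction for antibodies: "For ADAb however, data will only be mapped to scheduled site visits where ADAb levels are planned to be measured".

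SAP 9.2 also plans ASAS40-over-time figures in the FAS with NRI, by ADAb positive, ADAb negative and missing. One version uses AS0009 samples; the other uses both studies.

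**The concern.** The labels and the exclusion pull against each other. NRI in the FAS should keep a subject who has left and count that subject as a failure. A condition that requires a Week 48 antibody result removes the same subject from numerator and denominator alike.

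The exclusion may also be related to outcome, since Protocol 5.1 states "Subjects not responding to treatment may be withdrawn from the treatment and study at the discretion of the Investigator". If subjects with higher titers lose response and leave more often than others, the titer groups would look more alike than they are. This is the only planned display of response by antibody level, and assessing immunogenicity is a stated objective (Protocol 3.3). The SAP asks for no count of the excluded subjects, so a reader of the figure could not judge the effect.

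**Working it through.** The documents state no rate, sample size or power for this figure, so there is nothing to reproduce. The check traces the rules and then illustrates the size with assumed values.

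**Step 1: who is in the figure.** ADAb is sampled at entry and Weeks 12, 24, 36 and 48 (SAP 2.2.5). The ASAS components are collected at the same visits (Protocol 8.1, 8.3, 8.5). ADAb is also sampled at ET (Protocol 8.13), and the 21-day window in SAP 9.2 does not apply to ET samples. Weeks 36 and 48 are consecutive ADAb visits.

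| Subject | Week 48 ADAb | In the titer figure? | Week 48 ASAS40 under SAP 4.2.1 |
|---|---|---|---|
| Leaves at Week 20, ET sample | None (ET maps to Week 24) | No | Non-responder |
| Leaves at Week 30, ET sample | None (ET maps to Week 36) | No | Non-responder |
| Leaves at Week 40, ET sample | ET maps to Week 48 | Yes | See note |
| Leaves at Week 40, no ET sample | None | No | Non-responder if ASAS40 is also missing |
| In study, Week 48 ADAb missing | None | No | As observed, or NRI |
| In study, ADAb present, ASAS40 not derivable | Present | Yes | Non-responder |

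Note: ET efficacy data also map to Week 48. The text does not settle whether this subject is scored on the ET values (SAP 3.5) or as a dropout (SAP 4.2.1).

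**Step 2: how many.** The maximum N is 285 (SAP 2.4). Assume that leaving times are uniform over Weeks 0 to 48 and that every leaver gives an ET sample. Then (48 − 36)/48 = 25% of pre-Week-48 leavers are mapped to Week 48 and 75% are excluded.

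- 5% leaving: 285 × 0.05 = 14.25; × 0.75 = 10.7 excluded
- 10% leaving: 28.5; × 0.75 = 21.4 excluded
- 15% leaving: 42.75; × 0.75 = 32.1 excluded

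**Step 3: overall level.** If the excluded share d consists of NRI non-responders, displayed rate = NRI rate/(1 − d). With an assumed NRI rate of 60%:

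- d = 0.05 × 0.75 = 3.75%: 60/0.9625 = 62.3%
- d = 7.5%: 60/0.925 = 64.9%
- d = 11.25%: 60/0.8875 = 67.6%

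**Step 4: contrast by antibody status.** Let r be the response among subjects kept and d the share excluded in each group, all counted as failures. The figure shows r_pos − r_neg. NRI gives r_pos(1 − d_pos) − r_neg(1 − d_neg). The distortion, figure minus NRI, is r_pos·d_pos − r_neg·d_neg. All values below are assumed.

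| r_pos / r_neg | d_pos / d_neg | Figure (points) | NRI (points) | Distortion (points) |
|---|---|---|---|---|
| 60% / 60% | 10% / 10% | 0 | 0 | 0 |
| 60% / 60% | 15% / 5% | 0 | 51.0 − 57.0 = −6.0 | +6.0 |
| 60% / 60% | 20% / 5% | 0 | 48.0 − 57.0 = −9.0 | +9.0 |
| 60% / 60% | 5% / 15% | 0 | 57.0 − 51.0 = +6.0 | −6.0 |
| 45% / 60% | 10% / 10% | −15.0 | 40.5 − 54.0 = −13.5 | −1.5 |
| 45% / 60% | 20% / 5% | −15.0 | 36.0 − 57.0 = −21.0 | +6.0 |
| 45% / 60% | 5% / 15% | −15.0 | 42.75 − 51.0 = −8.25 | −6.75 |

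A loss is understated only when r_pos·d_pos exceeds r_neg·d_neg. In these scenarios the distortion runs from −6.75 to +9 points. Quartile cells may be small: with 10 subjects assumed in a cell, leaving out one failure turns 6/11 (54.5%) into 6/10 (60%).

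**The case against.** The strongest defence is that other outputs carry this information. Protocol 13.5 asks for ASAS40 against ADAb positivity over time, and the over-time figures provide it. In them, a subject with two or more positive samples stays in the positive group whatever is missing later, and so counts as an NRI failure after leaving. Subjects who cannot be classified get their own line unless they are 5% or fewer. That stands, with limits. Those figures are not by titer. A leaver with one positive sample and the rest missing is classed as negative. A leaver with no positives and two or more missing samples goes to the missing group, which may be omitted.

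It can also be said that the SAP states the exclusion openly, that NRI still acts on subjects with a Week 48 ADAb result but no derivable ASAS40, and that leavers with no valid post-entry efficacy measurement are outside the FAS anyway (SAP 3.6.3). All three are true, and the last makes the counts in the working upper-end figures. None of them returns the remaining early leavers to the denominator.

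Finally, withdrawal has many causes besides non-response (Protocol 6.3), and nothing in the documents links leaving to titer. The NRI contrast is therefore not a clean measure of antibody-related loss. This is a fair caution about interpreting either version.

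**Conclusion.** The point holds as a minor one. The titer figure conditions on a Week 48 or mapped ET antibody result, so most subjects who leave before about Week 36 are missing from it although SAP 4.2.1 counts them as non-responders. The displayed overall response is higher than the Week 48 NRI rate in SAP 8.2: about 2 to 8 points under the assumptions of 60% NRI response and 5% to 15% attrition. That direction assumes the excluded subjects are mostly NRI failures; subjects still in the study who only missed the ADAb sample could be responders. The between-group distortion can go either way and cannot be sized from the documents.

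A reader might infer that everyone who leaves before Week 48 disappears, that NRI has no role, and that any antibody-related loss of response is hidden. The documents do not support this. ET samples taken after the Week 36 visit map to Week 48. NRI still acts on some subjects in the figure. Loss among those who stay is shown. The over-time figures keep leavers with at least two positive samples. The primary safety variables and the secondary ASAS40 summary are not affected.

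**What to change.** In the Week 48-titer figure, replace the exclusion with a separate missing category that shows its n and NRI ASAS40 percentage, following the missing group in the over-time figures. Add a second version that classifies each FAS subject by the last available AS0009 ADAb result up to and including Week 48, with NRI applied to all; any subject with no AS0009 result goes in the missing category. Last available is preferable to highest titer, because the highest value tends to rise with the number of samples and would push subjects who stay into higher categories.

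The cost is a few lines of SAP text, one figure reprogrammed and one added, using samples already collected. The downside is that an earlier titer is less contemporaneous with the Week 48 response, which is why the Week 48-titer version should be kept alongside.

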10 SAFETY ANALYSES

AEs will be coded according to MedDRA.

AEs will be summarized by treatment group at completion of AS0008 and overall, by primary SOC, HLT, and PT in alphabetical order. This summary will include incidence, exposure-adjusted incidence rates (EAIRs) with associated 95% CIs, and exposure-adjusted event rates (EAERs) where the EAIR and EAER are expressed per 100 subject-years of exposure. Subject exposure at risk is defined in [Section 10.1](#).

Change from AS0009 Laboratory Baseline in laboratory variables (except CRP) will be summarized descriptively by visit and by treatment group at completion of AS0008 and overall.

Change from AS0008 Baseline in ECG and vital signs variables will be summarized descriptively by visit and by treatment group at completion of AS0008 and overall.

Safety variables will be reported for the SS. Key safety analyses will be repeated for both SS Sub-populations (see [Section 3.6.2](#)) and/or will include data from AS0008 for subjects who continued in to AS0009, as described below.

10.1 Extent of exposure

Study medication duration will be calculated for each of the following using the imputation rules in [Section 4.2.4](#) for partial treatment end dates:

- Total bimekizumab duration: Between the first dose of bimekizumab in AS0008 and last dose of bimekizumab in AS0009.
- Total duration on bimekizumab 160mg: Between the first and last dose of bimekizumab 160mg (in AS0008 or AS0009).

- Duration on bimekizumab 320mg: Between the first dose of bimekizumab 320mg in AS0008 and first dose of bimekizumab 160mg in AS0009 (calculated only for subjects who took bimekizumab 320mg in AS0008).
- Duration on bimekizumab 160mg in AS0009: Between the first and last dose of bimekizumab 160mg in AS0009.

The duration of exposure will be calculated as outlined in [Table 10–1](#).

Table 10–1: Study medication duration

Duration Category	Start date	End date	Study medication duration
Total BKZ duration	First dose of BKZ in AS0008	Last dose of BKZ in AS0009	End date – start date + 28 ^a
Total duration on BKZ 160mg	First dose of BKZ 160mg in AS0008 or AS0009	Last dose of BKZ 160mg in AS0009	End date – start date + 28 ^a
Duration on BKZ 320mg	First dose of BKZ 320mg in AS0008	First dose of BKZ 160mg in AS0009	End date – start date + 1
Duration on BKZ 160mg in AS0009	First dose of BKZ 160mg in AS0009	Last dose of BKZ 160mg in AS0009	End date – start date + 28 ^a
Subjects who died ^b	Start date for each option as above	Date of death	End date – start date + 1

BKZ=bimekizumab.

^a 28 days refer to one half-life of BKZ.

^b For subjects who died, the date of death will be used to replace the end date in the calculation of study medication duration only if the subject died within the dosing interval (i.e., within 28 days following the last dose [not applicable for duration on BKZ 320mg]) or if the subject died before dosing in AS0009 (for duration on BKZ 320mg). If the subject died more than 28 days after the last dose of BKZ in AS0009 the study medication duration will be calculated using the dosing interval of 28 days.

The exposure time at risk will be calculated as outlined in [Table 10–2](#).

Table 10–2: Exposure time at risk

Exposure Category	Start date	End date	Duration of Exposure
Total BKZ exposure	First dose of BKZ in AS0008	Last dose of BKZ in AS0009	Minimum of [(End date – start date + 140 ^a) +1] and (Date of last clinical contact ^b – start date + 1)

Table 10–2: Exposure time at risk

Exposure Category	Start date	End date	Duration of Exposure
Total exposure to BKZ 160mg	First dose of BKZ 160mg in AS0008 or AS0009	Last dose of BKZ 160mg in AS0009	Minimum of [(End date – start date + 140 ^a) +1] and (Date of last clinical contact ^b – start date + 1)
Exposure to BKZ 320mg	First dose of BKZ 320mg in AS0008	First dose of BKZ 160mg in AS0009 for subjects who were dosed in AS0009 ^c . Last dose of BKZ 320mg in AS0008 for subjects who were not dosed in AS0009	(End date – start date + 1) for subjects who were dosed in AS0009. Minimum of [(End date – start date + 140 ^a) +1] and (Date of last clinical contact ^b – start date + 1) for subjects who were not dosed in AS0009
Exposure to BKZ 160mg in AS0009	First dose of BKZ 160mg in AS0009	Last dose of BKZ 160mg in AS0009	Minimum of [(End date – start date + 140 ^a) +1] and (Date of last clinical contact ^b – start date + 1)
Subjects who died ^d	Start date for each option as above	Date of death	End date – start date + 1

BKZ=bimekizumab.

^a 140 days refer to 5 half-lives of BKZ.^b Date of last clinical contact for each subject is defined as the maximum of [last visit date including SFU visit (including unscheduled SFU visits), last AE start date (including imputed AE start dates), date of study termination or completion, last date of study drug administration following rules for partial treatment end dates as per Section 4.2.4].^c In the event that the first dose in AS0009 was more than 140 days after the last dose in AS0008, the exposure time at risk for 320mg will be calculated using AS0008 end date – AS0008 start date + 140 days.^d For subjects who died, the date of death will be used to replace the end date in the calculation of exposure time at risk only if the subject died within the ‘at risk’ interval (i.e., within 140 days following the last dose [not applicable for duration on BKZ 320mg] or if the subject died before dosing in AS0009 (for time at risk on BKZ 320mg). If the subject died more than 140 days after the last dose of BKZ in AS0009 the exposure time at risk will be calculated using the ‘at risk’ interval of 140 days. Note that date of death should be equivalent to date of last clinical contact.

In the event that a subject received an incorrect (unplanned) treatment sequence the calculations for study medication duration and exposure time at risk will be adjusted accordingly following the principles outlined above and this will be documented in the relevant dataset specifications.

Three summaries of exposure will be provided: two for exposure in AS0009 and one for exposure in AS0008 and AS0009 combined.

- For the AS0009 summary, durations of exposure and times at risk will be summarized by treatment group at completion of AS0008 and overall. This summary will be repeated by SS Sub-population.
- For the AS0008 and AS0009 combined table, the duration of exposure and time at risk for 'BKZ 160mg', 'BKZ 320mg' and 'BKZ Total' will be summarized. Subjects who took bimekizumab 320mg during AS0008 will contribute to all three columns. Subjects who did not take bimekizumab 320mg in AS0008 will contribute to the 'BKZ 160mg' and 'BKZ Total' columns.

The total study medication duration and total time at risk will be included in the exposure tables. These will be calculated by summing the study medication duration (or time at risk) across all subjects (per treatment group) and will be expressed in years and presented to 1 decimal place.

Start date of study medication in AS0008, start and end dates of study medication in AS0009, the durations of exposure and the times at risk will be listed.

10.2 Adverse events

An AE is any untoward medical occurrence in a patient or clinical investigation subject administered a pharmaceutical product that does not necessarily have a causal relationship with this treatment. An AE can therefore be any unfavorable and unintended sign (including an abnormal laboratory finding), symptom, or disease temporally associated with the use of a medicinal (investigational) product, whether or not related to the medicinal (investigational) product.

AEs that occurred during the AS0008 study and are ongoing at the time of enrolment (signed informed consent) in AS0009 will be captured in the AS0009 database and followed up until the AEs have resolved, have stable sequelae, the Investigator determines that it is no longer clinically significant, or the subject is lost to follow-up.

This follow-up requirement applies to AEs, SAEs, AEs of special interest (AESIs), and AEs defined as Safety Topics of Interest; further details regarding follow-up of Potential Drug-induced Liver Injury (PDILI) events are provided in Section 9.4.1 of the protocol. Information on SAEs obtained after clinical database lock will be captured through the Patient Safety database without limitation of time.

If an AE is ongoing at the end of the AS0009 study, follow-up should be provided until resolution/stable level of sequelae is achieved, or until the Investigator no longer deems that it is clinically significant, or until the subject is lost to follow-up. If no follow-up is provided, the Investigator must provide a justification. The follow-up will usually be continued for 20 weeks after the subject has discontinued his/her IMP.

All AEs occurring during the AS0009 study (i.e. after signature of the informed consent document) will be recorded in the eCRF. For each AE the following information will be recorded in the eCRF: AE term (verbatim term), date of onset, whether or not the AE was classified as a SAE, as an AESI, intensity, relationship to study medication, action taken with study medication, other action taken, outcome, date of outcome, and whether the AE led to study drug discontinuation or to study discontinuation.

The following code lists will be used for AE recording:

- Pattern of event: intermittent or continuous
- Intensity of event: mild, moderate or severe
- Relationship: related or not related
- Action taken with IMP: dose not changed, dose reduced, dose increased, drug temporarily, interrupted, drug permanently withdrawn or not applicable
- Outcome: resolving, not resolved, resolved, resolved with sequelae, worsened, fatal or unknown

AEs (including SAEs) are characterized as either non-treatment-emergent or treatment emergent according to the following criteria:

- Non-treatment emergent AEs are those with onset date after a 140-day period after the end date of study medication.
 - Any AE occurring more than 140 days after the last administration of study medication in AS0008 and prior to the first administration of study medication in AS0009 will also be considered as non-treatment emergent, and will therefore be excluded from the summary tables. Such events will be included in the listings.
- TEAEs are those with onset date on or after the start date of study medication in AS0009.
- Events that were ongoing at the end of AS0008 will have their treatment-emergent status taken from the AS0008 database.

For all AEs the following variables will be calculated (see [Section 10.2.1](#)):

- Duration.
- Time since first bimekizumab dose.
- Time since last/latest bimekizumab dose.

AE summaries will, in general, include only events with onset on or after the start date of study treatment in AS0009. Certain displays will be repeated including all AEs in AS0008 (with the exception of those with onset during placebo treatment) and AS0009 as outlined below. These displays will include only subjects from AS0008 who were enrolled in AS0009.

In general, the attributes of these events (for AEs that started and were resolved in AS0008) will be taken from the AS0008 database. However, the identification of Safety Topics of Interest will be made across all events in AS0008 and AS0009 using the criteria defined in this SAP.

For events which were ongoing at the end of AS0008, the following rules will be implemented:

- Onset date (and derived variables) will be taken from the AS0008 database
- End date, outcome, actions taken and seriousness will be taken from the AS0009 database.
- In order to ensure that AEs are not duplicated in the outputs these will be merged across the studies by Subject ID, verbatim term (AETERM), dictionary-derived term (AEDECOD), start date (AESTDTC), relationship (AEREL) and severity (AESEV) to create one record for the specific event.

Summaries of AEs in AS0008 and AS0009 will include AEs with onset on the first dose of bimekizumab in AS0008 up to 140 days after the last dose of bimekizumab in AS0009. AEs which occur on the day of a treatment switch will be considered to have begun on the previous treatment, with the exception of the following AEs which will be considered to have begun on the new treatment:

- Events that fulfill the anaphylaxis criteria for acute events (see [Section 10.2.3](#)).
- Events that fulfill the hypersensitivity reaction criteria for (see [Section 10.2.3](#)).
- Events with a HLT of “Administration site reactions NEC”.
- Events with an HLT of “Injection site reactions”.

AEs which occur on the first day of bimekizumab treatment in AS0008 following initial treatment with placebo will not be included in the summaries, unless they fulfill 1 of the 4 exception criteria above. AEs which occur after the last dose of bimekizumab in AS0009 and up to 140 days after the last dose of bimekizumab in AS0009 will be assigned to bimekizumab 160mg.

AEs will be presented as “number of subjects (percentage of subjects) [number of events]”. “[number of events]” will include all cases of an AE including repeat occurrences in individual subjects, while “number of subjects” will count each subject only once.

An overview of TEAE (number and percentage of subjects with any TEAE, serious TEAE, TEAE leading to study discontinuation, TEAE leading to permanent withdrawal of study medication, drug-related TEAE, severe TEAE, fatal AE [see note below], fatal TEAE and TEAE with missing seriousness) will be provided by treatment group at completion of AS0008 and overall. This summary will be repeated by SS Sub-population. It will also be repeated including all TEAEs in AS0008 and AS0009 reported for subjects in the AS0009 SS (with the exception of those with onset during placebo treatment) combined.

The category for fatal AEs will be based on all subjects enrolled in AS0009 in all the above summaries.

The following categories of TEAE will be summarized by MedDRA SOC, HLT and PT, including EAIR and EAER (calculated as described in [Section 10.2.2](#)), where all summaries refer to AEs reported in AS0009 only except where stated:

- All TEAEs by treatment group at completion of AS0008 and overall.
- All TEAEs by treatment group at completion of AS0008 and overall, by SS Sub-population.
- Serious TEAEs by treatment group at completion of AS0008 and overall.
- Serious TEAEs by treatment group at completion of AS0008 and overall, by SS Sub-population.
- All TEAEs in AS0008 and AS0009 by treatment at time of AE onset (BKZ 160mg, BKZ 320mg and BKZ Total).
- Serious TEAEs in AS0008 and AS0009 by treatment at time of AE onset (BKZ 160mg, BKZ 320mg and BKZ Total).

- All TEAEs AS0008 and AS0009 by timing of onset relative to ADAb status in AS0008 and AS0009. This will include columns for the following:
 - TEAEs starting before the first ADAb positive result in AS0008 and AS0009 (includes ADAb Categories 2b only)
 - TEAEs starting on the same date or after the first ADAb positive result in AS0008 and AS0009 (includes ADAb Categories 2b, 3b, 4b, 5b and 6b)
 - TEAEs for subjects who are ADAb negative at all time points in AS0008 and AS0009 (includes ADAb Categories 1b only)

Note that any TEAEs occurring for a subject who was ADAb positive at AS0008 Baseline will therefore all occur after ADAb positivity; such subjects will be excluded from the first column in the above table. Subjects in Category 9b (missing) will not be included in the table.

The following categories of TEAE will be summarized by MedDRA SOC, HLT and PT, by treatment group at completion of AS0008 and overall:

- TEAEs leading to study discontinuation and/or permanent withdrawal of study medication.
- TEAEs leading to permanent withdrawal of study medication.
- TEAEs with a fatal outcome.
- All TEAEs by maximum relationship.
- Serious TEAEs by maximum relationship.
- TEAEs with a fatal outcome by maximum relationship.
- All TEAEs by maximum intensity.
- Non-serious TEAEs reported by more than the reporting threshold of 5% of subjects. The cut-off will be applied before rounding on each treatment group and overall.

A further summary will be presented by treatment group at completion of AS0008 and overall displaying the frequency of TEAEs by descending frequency of PT.

An additional table will be presented by MedDRA SOC, HLT and PT, by treatment at time of AE onset (BKZ 160mg, BKZ 320mg and BKZ Total) for all TEAEs in AS0009 and all TEAEs that were ongoing from AS0008 at the time of the AS0009 EV. Ongoing TEAEs are defined as TEAEs that started prior to the AS0009 EV and continued after the first dose of study medication in AS0009.

Summaries will be based on treatment at onset and include columns for BKZ 160mg, BKZ 320mg and BKZ Total (where BKZ Total includes all other doses, if applicable, excluding placebo). Tables will include only n and %, the denominator (i.e. N) will be as for the current tables (total number of subjects receiving at least one dose for each column)

TEAEs classified as Safety Topics of Interest and associated tables are defined in [Section 10.2.3](#).

The following AE listings will be provided based on the ES:

- Glossary table for all TEAEs (this listing will include all events in AS0008 and AS0009 for subjects that were enrolled in AS0009 [with the exception of AEs with onset during placebo treatment]).
- All AEs (this listing will include all events in AS0008 and AS0009 for subjects that were enrolled in AS0009 [with the exception of AEs with onset during placebo treatment]).
- All SAEs (this listing will include all events in AS0008 and AS0009 for subjects that were enrolled in AS0009 [with the exception of AEs with onset during placebo treatment]).
- All AEs leading to study discontinuation.
- All deaths.

The following listings will be provided based on the SS:

- Serious Infections TEAEs.
- Fungal infectious disorder TEAEs.
- Opportunistic infection (including tuberculosis [TB]) TEAEs.
- Malignant or unspecified tumor TEAEs.
- Malignant tumor TEAEs.
- Adjudicated cardiovascular TEAEs by event type.
- Adjudicated cardiovascular TEAEs by event type for major adverse cardiac events (MACE)
- Adjudicated cardiovascular TEAEs by event type for extended MACE
- TEAEs identified for potential review by the Cardiovascular Event Adjudication Committee.
- Neutropenia TEAEs.
- Suicidal ideation and behavior TEAEs
- TEAEs identified for potential review by the Neuropsychiatric Adjudication Committee.
- TEAEs adjudicated by the Neuropsychiatric Adjudication Committee.
- Inflammatory bowel disease TEAEs.
- Hypersensitivity reaction TEAEs.
- Anaphylactic reaction TEAEs
- Hepatic events TEAEs.
- Hospitalization/Emergency Room Visits.

